EFFECT OF NON-INVASIVE MECHANICAL VENTILATION ON NEURORESPIRATORY COUPLING DURING EXERCISE IN PATIENTS WITH SEVERE CHRONIC OBSTRUCTIVE PULMONARY DISEASE

Version 5.0, Madrid 23/09/2019

BACKGROUND AND CURRENT STATUS OF THE ISSUE

In patients with chronic obstructive pulmonary disease (COPD), during exercise, limitation of expiratory flow and increased respiratory rate can decrease expiratory time, resulting in increased residual volume, a condition known as dynamic hyperinflation (O'Donnell, Revill et al. 2001). The inevitable consequence of this condition is an increase in intrinsic telexpiratory positive pressure (PEEPi) and increased work of breathing. Finally, the result is severe dyspnea during physical exertion that reduces exercise tolerance (Babb, Viggiano et al. 1991, Marin, Carrizo et al. 2001, Soffler, Hayes et al. 2017, Marrara, Di Lorenzo et al. 2018).

Recently, great interest has developed in the use of non-invasive mechanical ventilation (NIV) to increase physical capacity during exercise (Hill and Holland 2014, Ambrosino and Xie 2017, Furlanetto and Pitta 2017, Marrara, Di Lorenzo et al. 2018), because of evidence that assisted ventilation reduces muscle load, which would allow the patient to train with higher intensity exercises.

During physical exercise of COPD patients, who have increased respiratory work, there may be a redistribution of blood flow from the extremities to the respiratory muscles, which would induce early muscle fatigue in the extremities, a recognized cause of exercise disruption. This redistribution could, at least in part, be reduced if ventilation is assisted during exercise (Ambrosino and Cigni 2015), and prevention of exercise-induced diaphragmatic exhaustion through NIV has already been demonstrated in some studies (Babcock, Pegelow et al. 2002, Borghi-Silva, Oliveira et al. 2008).

As PEEPi and exhaustion of inspiratory muscles in COPD patients contribute to the development of dyspnoea, it is possible that NIV provides at least symptomatic benefit through muscle unloading and decreased work of breathing. By unloading the respiratory muscles, they may need less blood flow and thus avoid redistribution from the extremities that limits the patient's physical capacity (Ambrosino and Cigni 2015).

The message from these physiological studies is clear: NIV during exercise may reduce respiratory work and dyspnea, increasing exercise tolerance, but the available evidence is controversial. Some studies have found no benefit of NIV during exercise using a hybrid ventilatory mode of positive pressure proportional to patient effort and not a fixed support pressure (Bianchi, Foglio et al. 2002), while others have found an increase in exercise intensity in patients with NIV even with the same ventilatory mode (Hawkins, Johnson et al. 2002), compared to patients with spontaneous ventilation. However, two meta-analyses on the subject conclude that, given the small number of studies available and the small sample size, randomized clinical studies are necessary to determine the real effects of NIV in COPD and validate its widespread recommendation in rehabilitation programs (Menadue, Piper et al. 2014, Ricci, Terzoni et al. 2014). Since most patients with moderate and severe COPD are candidates for rehabilitation programs, and rehabilitation is an important component in the management of dyspnea (Ambrosino and Cigni 2015), the use of NIV during exercise is a major issue.

A recent study (Marrara, Di Lorenzo et al. 2018) demonstrated the effect of performing treadmill rehabilitation with the aid of NIV. Although inspiratory pressures were discrete (mean IPAP 12cmH₂O), an improvement in peak expiratory pressure, improved oxygen consumption and exercise capacity was demonstrated, compared with the spontaneous ventilation rehabilitation program.

Although it is widely accepted that awareness of increased muscular respiratory work by central breathing centers is important for the sensation of dyspnea, the identification of a reliable physiological measurement of the respiratory neural drive (RND) represents a significant challenge. In addition, we know that dyspnoea increases disproportionately when the ventilatory response is limited by mechanical alterations in the lungs (Scano, Innocenti-

Bruni et al. 2010), such as in COPD, a phenomenon known as neuroventilatory uncoupling (DNR)(Jolley, Luo et al. 2015).

Ventilation-related measurements do not adequately reflect the DNR in COPD patients, because their alterations in respiratory mechanics modify the relationship between the DNR and inspiratory flow. Nor can it be related to variables relating to respiratory system pressures, because these vary according to the contractile capacity of the respiratory muscles and their tension, properties that are independent of the DNR, especially in the presence of pulmonary hyperinflation (Cherniack and Snidal 1956).

But recently the measurement of diaphragmatic contraction using an oesophageal probe with electrodes, diaphragmatic electromyography (EMGdi) (Sinderby, Spahija et al. 2001, Spahija, de Marchie et al. 2010, Reilly, Ward et al. 2011) This has allowed the precise quantification of DNR, since a measure is obtained that is, from a neurophysiological point of view, closer to the generation of the respiratory impulse than changes in pleural pressure (Luo, He et al. 2014). The measurement of DNR by EMGdi has demonstrated a close relationship between the increase in dyspnea, measured by the Borg scale, and DNR. The measurement of the respiratory minute volume is poorly related to dyspnea because under physical effort, and once the decoupling point is exceeded, despite the compensatory increase in respiratory rate and muscle effort and respiratory drive, the minute volume reaches a plateau. Despite the parallel increase in dyspnoea and neural drive, no increase in minute volume is obtained (Jolley, Luo et al. 2015).

The study of DNR behaviour, as described above, has been conducted in patients with severe COPD at rest and during physical exercise (Jolley, Luo et al. 2015), but has not been studied in patients with WV. It is possible that WV, by increasing alveolar ventilation and tidal volume, may modify the respiratory mechanical characteristics responsible for VN, and we have therefore set out to investigate the behavior of VN in patients with COPD and WV at baseline and during exercise.

The measurement of the neural drive from diaphragmatic electromyography is considered the "gold standard" method but has a number of associated problems. Perhaps the most relevant is the invasiveness of the method: it

requires the use of an esophageal probe with multiple electrodes, whose insertion may be uncomfortable for the patient.

Recently, the use of parasternal electromyography has been proposed as a surrogate marker of diaphragmatic muscle electrical activity with a good correlation to diaphragmatic electromyography through an esophageal catheter (Lin, Guan et al. 2019). Its use, in patients at rest, seems promising to obtain a signal with clinical relevance, having been proposed as a marker of increased respiratory muscle effort in stable and acute COPD (Murphy, Kumar et al. 2011), in pediatric population with cystic fibrosis (Reilly, Ward et al. 2011) and in other respiratory patients. Its use during exercise is controversial, since the muscle activation of the shoulder girdle that occurs when grasping the handlebars of the bicycle conditions an interference in the registration of the sternal muscles (Ramsook, Mitchell et al. 2017). The use of recumbent bicycles is proposed to keep the arms at rest and limit this interference.

Finally, in recent years a new method of ventilatory support has burst onto the scene, the high flow nasal goggle (HNFG), whose usefulness in the field of acute respiratory failure, especially hypoxemic, has led to its widespread use in acute units. There is little experience with the use of this technique in a stable COPD situation and even less during rehabilitation. However, it has been shown to improve dyspnea, exercise capacity and oxygenation during effort. (Cirio, Piran et al. 2016). It seems that, given that it is capable of generating a certain PEEP (Okuda, Tanaka et al. 2017) effect, it may be useful to compensate for the dynamic hyperinflation generated in COPD patients, and therefore, neurorespiratory coupling.

HYPOTHESIS

Theoretical hypothesis: non-invasive mechanical ventilation can correct the neurorespiratory decoupling that develops in patients with severe COPD during physical exercise.

Operational hypothesis: non-invasive mechanical ventilation reduces the difference that develops during exercise between the respiratory neural drive and the respiratory minute volume, which causes neurorespiratory decoupling.

Statistical hypothesis:

H0: no difference in the development of neurorespiratory decoupling in COPD patients under physical exercise with spontaneous or mechanically assisted ventilation. ($NVU_{Vm} = NVU_{esp}$)

H1: neurorespiratory decoupling is less in COPD patients under physical exercise with non-invasive mechanical ventilation than in the same patients with spontaneous ventilation. ($NVU_{Vm} > NVU_{esp}$)

Objectives

Main objective:

- Demonstrate that non-invasive mechanical ventilation during incremental exercise decreases neurorespiratory decoupling in patients with very severe COPD.

Secondary objectives:

- To study the behaviour of dyspnoea with the use of non-invasive mechanical ventilation during exercise in patients with severe COPD
- To study the behaviour of residual volume, air entrapment and exercise-induced hypercapnia in patients with severe COPD on non-invasive mechanical ventilation

METHODS

Population

Inclusion criteria:

- Patients with severe COPD or Cystic Fibrosis (with obstructive pattern and air entrapment) on the waiting list for lung transplant, assessed by the Pulmonary Transplant Unit of the Hospital Universitario 12 de Octubre. In these patients, the exhaustive study they have undergone for the assessment of the indication for transplant, allows us to rule out interference in the results of this study due to comorbidities.

- Meet GOLD diagnostic criteria for COPD, and evidence of air entrapment plethysmography (residual volume greater than 120% of theoretical)
- Evidence of developing dynamic air entrapment by analyzing flow/volume curves during physical exercise.
- Patients already adapted to non-invasive mechanical ventilation at home (NMV) as a bridge to transplantation To avoid an extra intervention, those patients previously adapted to MDM, who have their own ventilation equipment, are acclimatized to its use and comply with this treatment, and have not suffered side effects that have contraindicated its use, will be included.

Exclusion criteria:

- Presence of uncontrollable comorbidities that limit the patient's capacity for physical effort (uncontrolled ischemic heart disease, severe pulmonary hypertension, neuromuscular pathology).
- Refusal of treatment with non-invasive mechanical ventilation, or inclusion in the study.

- Inability to perform the proposed exercise under basal conditions and with ventilation.

Ethical aspects

The study protocol has been approved by the Research Ethics Committee of the CEIC of the Hospital 12 de Octubre (resolution 18/025). Attached is informed consent. Participation in this study is completely voluntary, and does not affect the assessment of the patient on the transplant waiting list. From the point of view of confidentiality, compliance with the provisions of the LOPD 1.5/1999 will be ensured. Specifically, a database will be generated with a consecutive number as the only data identifying the patient. The correlation between the number of inclusion in the study and the number of the clinical history (as a unique identifier) will be stored in a database located in the folder of the Pneumology service in the "Y" server, with access protected by a password, only authorized to the two investigators of the work ([name] and [name]).

The intervention on the patients does not pose any risk (derived from the determination of surface electromyography) and only consists of the measurement of muscle activity during basal effort, with NIV and with high-flow nasal glasses, in a similar way to how rehabilitation of these patients is currently carried out, and within the usual rehabilitation program.

Studio design

Experimental, longitudinal, prospective and controlled study, with a branch and comparison before/after the same individuals.

Variables and measurements

First visit, baseline situation (coinciding with scheduled review in ventilation or transplant consultation or rehabilitation):

Medical history: smoking history (packet)

Anthropometric variables: age, weight, height, BMI.

Functional variables: BODE, BODEx, FEV1 (%), FVC (%), VR, TLC, DLCO, DLCO/VA Basal arterial blood gas and basal mean tcpCO2.

Clinical variables: measurement of dyspnea using Borg and MRC scales.

Checking inclusion/exclusion criteria and signing IC

The usual pre-transplant respiratory rehabilitation program includes 24 sessions, with a frequency of 2 sessions per week, in which it is performed:

- Warm-up exercises, elongations of spine, thorax and shoulder girdle.
- Respiratory physiotherapy exercises.
- Upper limb strengthening with progressive weight dumbbells (80% of 1RP 3 sets of 15 repetitions for biceps, triceps and deltoid)
- 30 minutes of training in recumbent cycloergometer. Exercise at constant load with ascent ramp 5 W/min until the plateau phase in load of 60% to 80% of the maximum load achieved in the Incremental stress test and cooling phase until the exercise is stopped.
- Cooling and relaxation exercises to recover from basal rest.

Second visit, fixed-duration intervallic exercise with spontaneous ventilation

- **INCREMENTAL STRESS TEST ON CYCLOERGOMETER**
- With this test, the exercise to be performed by the patient will be individually prescribed. It is part of the usual care activity in the respiratory rehabilitation unit, and it allows to determine the level of exercise that the patient tolerates.
- The test will be started by explaining to the patient what it will consist of, showing him/her the Borg's fatigue and dyspnea measurement scale modified to make him/her familiar with it. With the patient monitored (Oximetry, EKG, blood pressure, watt load) the test is started, supervised at all times by the Rehabilitation Doctor in the Lung Rehabilitation room. We will ask at the beginning of the test and every minute as well as at the end of the perception of dyspnea and fatigue.
 - 3 minutes rest on the cycloergometer with the patient seated
 - 3 minutes of free pedaling without load
 - Exercise with an increase in the ramp load of 10 watts every 3 minutes, until the test is stopped due to the patient's symptom limitation or objective data on their monitoring that force us to stop it:
 - MMII muscle fatigue limit
 - Severe dyspnea preventing you from continuing (modified Borg dyspnea scale of 0-10)

- Heart arrhythmia maintained.
 - Tachycardia exceeding 80% of the calculated FCmax (220-age)
 - Dizziness, instability, chest tightness.
 - Desaturation (<85% during exercise despite correct oxygen intake or <90% in patients with PTH)
- *Third visit, exercise at constant load, of fixed duration with spontaneous ventilation:*
 - 10 minutes of constant exercise will be performed, at 75% of the maximum tolerated load as determined in the second visit, by the rehabilitation physician.
 - We will insist on maintaining a constant pedaling cadence, between 35 and 40 cycles per minute.
 - It's registered:
- Neuro-respiratory coupling: NVU: $\text{EMGDimax\%}/\text{Vt}$. To determine the neurorespiratory coupling (NVU variable) the peak value (above the baseline) of the maximum muscular activity (averaged by square root of the EMG value in mV) both diaphragmatic (EMGDimax) and parasternal (EMGparamax) in the maneuvers of maximum voluntary ventilation and maximum inspiratory pressure (MIP) will be taken. On that value, taken as 100%, the average value of EMGpara and standardized EMGdi (RMS) in each ventilatory situation (spontaneous or low NIV ventilation) will be calculated. At each point of effort (in each minute of the exercise protocol) the ratio between the standardized EMG value (parasternal and diaphragmatic) and the tidal volume (obtained by integration of the flow signal by means of a pneumotachograph connected to the MV-in NIV circuit or an oronasal airtight mask-in Vesp) shall be measured. To facilitate the interpretation of the exhaled VC, a non-leak mask with the intentional leak connected to the circuit shall be used before the pneumotachograph.
- The degree of dyspnea will be determined with a Borg and Analog-Visual scale at 60" of effort
- The entire effort protocol will be monitored by TCP CO_2

- Total pedaling time and number of stops will be collected.
- At the end of this second visit, after about 20 minutes of rest, an exercise of about 10 minutes at constant load will be started to adjust the NIV parameters.
 - Based on the previously titrated home parameters, the inspiratory trigger is adjusted and EPAP is progressively increased until ineffective efforts are eliminated and trigger delay is minimized, and support (IPAP) is increased until a subjective decrease of at least 20% in the mean RMS value is achieved or until patient tolerance limits it.

Third visit, exercise with non-invasive mechanical ventilation:

- Effort protocol: it will be done in a similar way to the one done in spontaneous ventilation with similar calculations and measurements.
- In this third visit, exercise will be performed under non-invasive ventilation
- Ventilator programming: the parameters set in visit 2 will be used, recording the changes made with respect to the previous home programming.
- It will be performed at the same load in W as the test in spontaneous ventilation, maintaining a constant pedaling frequency between 35 and 40 cpm.
- They will be collected as other variables:
 - Rate of asynchronies during effort and % of ineffective effort
 - Neuro-respiratory coupling: NVU: EMGDimax%/Vt
 - Borg in times of 60" effort
 - TcpCO₂ final

- ETCO₂ final effort
- Number of stops and total pedalling time.

Fourth visit, exercise with high flow oxygen therapy:

Within the rehabilitation program, and as with mechanical ventilation, the patient will be offered exercise under high flow oxygen therapy, at constant flows of 50lpm and with FiO₂ adjusted according to SPO₂, to obtain a constant saturation between 92 and 94%. The same load and pedaling frequency will be maintained, with similar variables collected.

In summary, the included subject is scheduled for 4 study related visits: baseline, exercise level determination, spontaneous exercise, NIV exercise and high flow exercise. These visits fall within the normal care process of the pre-transplant rehabilitation program, not requiring additional patient visits for the study. The only difference with the care process is that neurorespiratory coupling (EMG for and exhaled flow) will be measured during exercise. The exercise program is the same that would have to be performed during conventional rehabilitation. Currently, the use of NIV or high flow during rehabilitation is routine, but the objective is to measure the physiological effect of rehabilitation, in a non-invasive way.

Statistical analysis

The statistical program SPSS 22.0 will be used for the analysis of the variables studied, to estimate the measures of centralization and dispersion of the results of the tests carried out and for multivariate analysis and correlations between the variables.

The NVU variable will be compared by means of a single-factor ANOVA with repeated measurements between the spontaneous and non-invasive ventilation determinations.

A difference of more than 20% is expected to be found in this value. It will be considered significant if $p < 0.05$.

The remaining secondary variables will be compared by t for repeated samples once their normal distribution has been confirmed.

Sample size calculation:

According to previously published work (Jolley, Luo et al. 2015), all COPD patients expressed neuro-respiratory decoupling. Assuming a 10% decrease in NVU as clinically significant, with a 95% confidence level (alpha 5% error) and a power of 80% (1-beta), assuming 5% losses, a required number of 18 patients is calculated. The sample size calculator for ANOVA provided by <http://powerandsamplesize.com/> has been used.

Potential limitations

- Measurement of neurorespiratory decoupling: in general, there are works that have questioned the reliability of EMG measurement for subrogation of EMGdi in conventional cyclo-ergometers, given the activation that the handlebar attachment induces in the parasternal musculature (Ramsook, Mitchell et al. 2017). Therefore, in order to minimize this effect, the use of a recumbent bicycle (there are 2 available in the rehabilitation room) is proposed, without arm support, which would be relaxed along the thorax.
- The use of an oronasal mask without leakage; placing the leak in the circuit, can eventually facilitate re-inhalation. This effect is expected to be minimal at the pressures expected to be used, and this variable will be continuously monitored by T_{CO2} . However, in spontaneous ventilation, given the severity of the obstruction to flow presented by patients, the addition of a pneumotachograph may generate greater inspiratory resistance and worsen tolerance.
- Need to have personnel trained in performing electromyography of respiratory muscles.
- Recruitment: this is usually a handicap in this type of study, but access to a population of severe COPD on a lung transplant waiting list makes recruitment much easier. They are patients already followed up in the ventilation and transplant clinic.

- NIV adaptation and tolerance, since the study population will already be adapted to a respirator, adaptation and synchronization are not expected to be a problem in this case.

Work Plan

- February-March 2018: final study protocol, drafting of the IC, approval by CEIC.
- March-April 2017: identification of candidates, assignment of test dates
- April 2018- September 2018: stress tests
- September 2018 - December 2018: analysis of results.
- January 2019 - March 2019: drafting of originals for publication

ESTIMATED BUDGET

Description	Amount
• Database design and maintenance	2.000€
• Final statistical analysis	2.000€
• Presentation of results at conferences and publication expenses	3.000€
• Data analysis of respiratory physiological variables: Powerlab 16 channels	12.000€
• Pulmonary Function Equipment: Respiratory and Exercise Physiology: Exhaled Volume per Minute (V·E) Oxygen Consumption (V·O ₂) Carbon Dioxide Production (V·CO ₂) Respiratory Exchange Rate (RER)	8.000€
• Transcutaneous capnography equipment	8.000€
• Indirect expenses foundation (10 %)	3.500€
Total	38.500€

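### Off-line processing of the exercise EMG is neither masked to ventilatory condition nor tied to fixed averaging windows and artefact rules, which leaves avoidable room for bias in the primary endpoint

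*Combined protocol and SAP*

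**What the plan says.** The Variables and measurements section defines NVU as "the ratio between the standardized EMG value (parasternal and diaphragmatic) and the tidal volume", taken at each minute of exercise. Two EMG quantities enter it.

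- **The 100% reference.** This is "the peak value (above the baseline) of the maximum muscular activity", and the protocol adds that it is obtained "in the maneuvers of maximum voluntary ventilation and maximum inspiratory pressure (MIP) will be taken". Whether these manoeuvres are done once per patient or at each visit is not stated.
- **The exercise value in each condition.** Here the text calls for "the average value of EMGpara and standardized EMGdi (RMS) in each ventilatory situation".

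For the NIV test the protocol says only that "it will be done in a similar way to the one done in spontaneous ventilation with similar calculations and measurements". Studio design describes a single group compared with itself before and after. Statistical analysis compares spontaneous with non-invasive ventilation by repeated-measures ANOVA and expects a difference above 20%. Sample size calculation uses a 10% decrease.

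No section mentions masking, an independent reader, an averaging window, a breath-selection rule, an artefact rule or a fixed processing algorithm. Potential limitations covers parasternal interference and the need for trained EMG staff, but not bias in processing.

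**The concern.** Neither patients nor staff can be masked while a mask and ventilator are in use. The recordings, however, can be coded before they are processed, and the plan does not do this. The exercise RMS depends on which parts of the signal are kept. The protocol itself says that shoulder-girdle activity contaminates the parasternal signal and that the recumbent bicycle is chosen to minimise this, so some rejection of artefact is likely to be needed.

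Expectation is also strong. Before the NIV test, the same signal is watched for a fall of at least 20% during ventilator adjustment (unless tolerance ends the adjustment first), and the analysis section expects a fall of similar size in NVU. A processor who knows the condition could, without intending to, keep quieter segments under NIV or noisier ones under spontaneous breathing. With two conditions and 18 patients, a small consistent shift of this kind cannot be told apart from a treatment effect.

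**Working it through.** **1. Where processing can act differently by condition.** Write E for exercise RMS, M for the maximal reference and V for tidal volume, so NVU = (E/M)/V. The contrast between conditions is

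NVU(NIV)/NVU(spont) = [E(NIV)/E(spont)] × [M(spont)/M(NIV)] × [V(spont)/V(NIV)].

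If one M per patient serves both conditions, the middle term is 1, and an error in the peak or baseline of the reference scales both NVU values equally. It can favour one condition only if M is taken again at each visit, which the protocol leaves open. The condition-specific room for choice lies in E.

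**2. How a shift in E carries through.** At fixed V and M, replacing E(NIV) by E(NIV) × (1 − b) multiplies NVU(NIV) by (1 − b). With no true effect and b = 5%, the ratio is 0.95, an apparent 5% decrease. With a true 10% decrease it is 0.90 × 0.95 = 0.855, an apparent 14.5% decrease.

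**3. Size against the plan's own yardsticks.** The documents give no reader variability, so b = 3-5% is an assumption.

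- Against the 10% decrease in Sample size calculation: 3/10 = 30% to 5/10 = 50%.
- Against the 20% in Statistical analysis: 3/20 = 15% to 5/20 = 25%.

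**4. The plan's sample size.** The figure of 18 cannot be reproduced, because no SD or within-patient correlation is given. It can only be solved backwards. With 5% losses, 17/0.95 = 17.9, which rounds up to 18, so take 17 evaluable patients. A two-level repeated-measures ANOVA is equivalent to a paired t test. With 17 pairs, two-sided 5% and 80% power, the required standardised difference is 0.724, so a 10-point decrease implies an SD of paired differences of 10/0.724 = 13.8 points (spontaneous NVU = 100).

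**5. Effect on false positives.** Assume no true effect, 17 pairs and a two-sided 5% test. The noncentrality is (b/SD) × √17. For b = 5 and SD = 13.8 it is 0.362 × 4.123 = 1.49. The probability of a significant result in favour of NIV is:

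| SD of differences | no bias | 2 points | 3 points | 5 points |
|---|---|---|---|---|
| 10 | 2.5% | 11.8% | 21.3% | 49.1% |
| 13.8 | 2.5% | 8.1% | 13.2% | 28.9% |
| 20 | 2.5% | 5.8% | 8.4% | 16.1% |

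These figures illustrate sensitivity to a consistent shift. They do not estimate any shift in this study. Masking would not change the required sample size.

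**The case against.** The best counter-argument is that manual reading is an inference. RMS is computed from the signal, the ratio is taken every minute, and the budget includes a 16-channel acquisition system. If processing is automatic with fixed settings, a processor has little room to influence it. This is right as far as it goes: the documents do not say whether processing is manual or automatic, and a fully pre-set algorithm would close most of the gap. But none is specified, so the protection is not in the plan.

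A second argument is that masking may fail, because the breathing pattern can reveal NIV or the processor may have run the sessions. This also stands. It is the reason to pair coding with a fixed rule.

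Two stronger readings are tempting and should not be made.

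- A reader might infer that the plan itself calls the endpoint reading subjective. The word occurs only in the ventilator adjustment step, where "support (IPAP) is increased until a subjective decrease of at least 20% in the mean RMS value is achieved" or tolerance limits it. It does not describe how NVU is read. That step shows that the processor has seen the signal under NIV and knows what to expect. The use of the same signal to adjust support is a separate question, which masked processing would not touch.
- A reader might infer that peak and baseline are set by eye in each condition. The text places them in the maximal manoeuvres that define the 100% reference, and the value taken in each condition is an average RMS.

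**Conclusion.** The concern holds in a limited form. The numerator of the primary endpoint comes from exercise EMG recordings whose processing is neither masked nor governed by stated windows and artefact rules, in an open comparison with a clear expectation. Any condition-dependent shift enters NVU in full at fixed tidal volume.

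The size is unknown. The 3-5% range is an assumption, and the false-positive figures rest in addition on an SD solved backwards from the sample size. The documents do not show that such bias will occur or that processing is manual. This is a cheap improvement to the conduct of the analysis and not a defect that invalidates the design.

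**What to change.** Add to Variables and measurements:

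1. Exercise EMG is processed off-line from recordings under random bout codes, with the EMG channel separated from pressure and flow.
2. One pre-set rule, or a fixed algorithm, defines averaging windows and artefact rejection and applies to all bouts.
3. EMG values are locked before tidal volume and condition are merged.
4. One maximal reference per patient is used for both conditions. If it is repeated at each visit, it is read under the same coding.
5. Someone already on the study team, other than the EMG processor, holds the code.

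The cost is a coding and export step and the time to write the rule. No patient, visit, test or clinical procedure changes, and no added staff are needed. The limit is that masking is imperfect if the breathing pattern reveals NIV or the processor ran the sessions. In that case the fixed rule is the main protection, and the report should say so.
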